## EXPERIMENTAL DESIGN AND METHODS

## **Rationale:**

In our preliminary studies, we demonstrated that saRBCs (but not fresh RBCs) impair NO-mediated vasodilation when studied using *in vitro* models as well as in hospitalized transfusion recipients. Some limitations of studying transfusion outcomes in hospitalized patients include the heterogeneity of this population, unpredictable times of transfusions, urgent/emergent circumstances, and a lack of standardization of inpatient covariates including time of day, diet and other associated therapies. Vascular tests (FMD and PAT) and measures of circulating NO, oxidative stress and inflammation are sensitive to co-morbidities, diet and medications. Finally, dynamic changes in patients' condition can also potentially confound experimental results. Conversely, transfusion studies can be performed in healthy volunteers. However, these subjects rarely have underlying endothelial dysfunction (which may synergize with saRBCs and magnify their effects on NO bioavailability) and for ethical reasons cannot be rendered anemic or transfused with allogeneic blood. Thus, transfusion effects in healthy volunteers may not necessarily be reflective of outcomes seen in sick patients.

In order to overcome these limitations, and to investigate the relationships between blood storage, reduced NO bioavailability, impaired vasodilation, and physiologic outcomes of transfusion, we propose to investigate the effects of saRBC transfusions in a chronically transfusion-dependent but ambulatory population. This approach has the following advantages: 1) these patients are stable over the course of days to weeks, 2) studies are performed under conditions of controlled diet, circadian rhythms, medications, etc., 3) the same subject receives both fresh and saRBCs in a randomized cross-over study design (see schema in Fig 4), and 4) because these patients are ambulatory, they can undergo cardiopulmonary exercise testing. Successful completion of the proposed studies will advance our understanding of mechanisms underlying the adverse events and functional consequences of saRBC transfusion and validate a model for subsequently evaluating potential treatments and storage techniques to reverse saRBC-mediated impairments (the latter objectives are beyond the scope of the present investigations).

## **Specific Aims:**

**Aim 1:** To assess the effects of fresh vs. saRBC transfusions on NO-dependent endothelial function in chronically anemic adults using: 1) flow mediated dilation (FMD) and 2) reactive hyperemic index (RHI) measured by pulsatile arterial tomography (PAT). The primary endpoint of this Aim is the change in FMD with fresh vs. saRBC transfusion; The secondary endpoint is change in RHI.

**Aim 2:** To assess the effects of fresh vs. saRBC transfusions on functional exercise capacity and oxygen carrying capacity by cardiopulmonary exercise testing. The primary endpoint is the change in peak oxygen consumption (VO2Max) after transfusion.

**Secondary endpoints** for the above Aims are changes in metabolic markers before and after transfusion/exercise: inflammation (IL-2, IL-6, hsCRP), oxidative stress (glutathione/glutathione disulfide and cysteine/cystine redox potentials), and nitric oxide metabolites (nitrite, nitrate, SNO-Hb and SNO-thiols).

**Hypotheses:** In patients with chronic transfusion-dependent anemia, transfusion of saRBCs will impair vascular reactivity compared to transfusion of fresh RBCs (Aim 1). Impairment of NO-mediated vasodilation will be associated with decreased exercise tolerance and peak oxygen consumption (VO2Max) following saRBC transfusion as compared to fresh RBCs (Aim 2), and will be associated with increased systemic oxidative stress and inflammation, and decreased circulating NO metabolites (Secondary endpoints).

[figure not shown]
**Subject Population:** Twenty-four subjects diagnosed with stable transfusion dependent anemia will be recruited and undergo a screening health questionnaire and physical examination to ensure eligibility. All subjects will provide informed consent prior to entry into the study. We will recruit adult subjects without preference to any race, gender or socioeconomic status. [name] translational research group in the Department of Cardiology regularly enrolls patients into clinical studies, and has experience consenting patients, randomizing them to study arms, and performing study protocols including the use of these non-invasive assays. This clinical research team oversaw execution of the clinical study comparing fresh vs. saRBC transfusions in hospitalized patients described in the preliminary results. Furthermore, we have also consulted with our Hematology colleagues, and have identified a large number of potential subjects who fit our criteria for this study. The proposed study has been approved by the Emory IRB.

**Eligibility Criteria:** Male or female volunteers age 21-80 with any condition resulting in RBC transfusion-dependent anemia will be eligible to participate. Participants may receive either 1- or 2-unit transfusions as required clinically so long as their transfusion requirement is stable throughout the study period.

**Ineligibility Criteria:** Age <21 or > 80 years, pregnancy, acute infection in previous 4 weeks, active substance abuse within the past year, inability to give informed consent, inability to return for follow-up or the presence of alloantibodies that would limit the blood bank's ability to obtain correctly aged RBC units. Participants with contraindications to cardiopulmonary exercise testing may be allowed to participate in the other study aims.

**Study Design:** Studies will be performed in a temperature-controlled vascular laboratory in the outpatient unit of the Clinical Research Network, ACTSI, at Emory University Hospital after an overnight fast. After providing informed consent, subjects will be randomized to receive their next clinically-indicated outpatient transfusion with fresh (<10 days old) blood or storage-aged (>21 day old) blood. Following their first transfusion, subjects will be crossed-over to receive the opposite aged product. Subjects and individuals conducting and interpreting experimental tests will be blinded to the age of RBC units. To maintain safety, clinical staff will not be blinded. All subjects will receive clinically indicated transfusions with cross-matched, leukoreduced AS1 units of packed RBCs from available blood bank inventory. The effects of RBC transfusion on blood flow and peripheral O2 delivery will be directly tested in the 24 volunteers using non-invasive assessments of endothelial function including: brachial artery flow-mediated dilation (FMD) and pulsatile arterial tonometry (PAT). Symptoms of fatigue and anemia will be objectively assessed at every visit using the self-administered FACT-An questionnaire (Functional Assessment of Cancer Therapy – Anemia). Vascular function will be assessed prior to transfusion as well as 1 hour and 24 hours after blood transfusion. Concurrently, subjects will undergo cardiopulmonary following each transfusion. Blood samples will be obtained at baseline, prior to and following each transfusion and from each unit transfused to perform metabolic marker testing.

**Study Schedule (Figure 4, below):** Each subject will be studied over a total of 4 visits, as shown in the Figure and described below.

**Screening:** Subjects will be screened with history and physical for inclusion and exclusion criteria and provide written consent. Subjects to meet inclusion and exclusion criteria, and give consent, will be randomized into either Group A or Group B.

**Visit #1 (Transfusion #1):** Subjects will return fasting to receive a scheduled, clinically-indicated RBC transfusion. Depending on their randomization to Group A or B, they will receive either fresh or saRBCs; an infusion pump will be used to administer the blood over a 1 hour period. FMD and PAT and will be performed and blood samples will be obtained for measurement of oxidative stress and other metabolic markers prior to and 1 hour following RBC transfusion.

**Visit #2 (Post-transfusion #1):** Subjects will return fasting the day following transfusion. FMD and PAT will be performed and blood samples will be obtained. CPX will be performed. The visit #3 (and #5) time points are important to this study since our preliminary data showed that impairment of NO-mediated vasodilation by saRBC transfusion was greatest 24 hours after transfusion.

**Visit #3 (Transfusion #2):** Visit #3 will recapitulate Visit #1 except that subject will receive the opposite aged product, as shown in the cross-over study design schema (Fig 4).

**Visit #4 (Post-transfusion #2):** Visit #4 will recapitulate Visit #2.

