**Impaired FMD responses in hospitalized patients transfused with saRBCs but not fresh RBCs.** As a extension of the *in vitro* aortic ring assays, and as part of a larger NIH funded investigation into the adverse effects of saRBC transfusions, we have also successfully studied the vascular effects of fresh RBCs vs. saRBCs on inpatients receiving medically indicated blood transfusions for anemia. After informed consent, subjects were randomized to receive either a fresh (<10 days old) or aged (>21 days old) blood transfusion. Endothelial function was assessed by FMD of the brachial artery prior, during, 1 hour after, and 24 hours following transfusion. Data were analyzed using a linear mixed effects model.

The 45 subjects who have completed the study had a mean age of  $58.5 \pm 13$  (SD). 52% were male and 50% were white. There were no differences in demographics, CVD risk factors, known CVD, amount of RBCs transfused, or baseline FMD between groups. Mean age of RBC units was  $9.1 \pm 3.1$  days and  $29.8 \pm 5.7$  days in the fresh and saRBC groups, respectively. As compared to pretransfusion FMD results, patients receiving fresh RBCs had no significant change in FMD at any time point either during or after transfusion ( $p > 0.05$ ; Fig 3, black bars). In a marked decrease at 1 hour post-transfusion (which did not reach statistical significance,  $p > 0.05$ ); however, by 24 hours after transfusion the continued reduction in FMD was statistically significant ( $p = 0.037$ ; Figure 3, white bars; manuscript in preparation). These inhibitory effects of saRBCs, but not fresh RBCs, on NO-mediated vasodilation in hospitalized patients are consistent with our *in vitro* studies shown above (Figs 1 and 2), further supporting the INOBA hypothesis. Unlike recently published reports which found no vascular effects of either fresh or saRBC transfusions in healthy recipients, we studied ill, anemic patients receiving standard allogeneic transfusions, thus underscoring the likely importance of recipient factors to adverse effects of saRBC transfusion.

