**Figure 3: Change in % FMD with pRBC Transfusion**

\* p<0.05 for change from baseline FMD

**Cardiopulmonary exercise testing in peripheral arterial disease.** As part of an unrelated NIH funded study in patients with peripheral arterial disease (PAD), our group has studied an intervention (GM-CSF injected twice weekly) to improve collateral blood vessel formation and lower extremity blood flow in patients with PAD and claudication symptoms. The primary outcome is peak treadmill walking time at 3 months. The hypothesis is that GM-CSF will stimulate increased numbers of endothelial progenitor cells (EPCs), which are stem cells destined to form endothelium, thus improving blood flow and oxygen delivery. As a secondary outcome in this study, cardiopulmonary exercise testing, including measurement of VO2Max was completed on each participant at baseline and at 6 months. 124 of the recruited participants had VO2Max results at baseline and 3 months available for review. The mean $\pm$ SD VO2Max was 1202 $\pm$ 347 ml/min and 1236 $\pm$ 369 ml/min at baseline and 3 month follow-up, respectively, demonstrating a significant 2.83% increase ( $p=0.021$ ) in VO2Max across all 124 participants. Because the study is ongoing, these results cannot yet be divided into treatment arms to determine whether GM-CSF was more effective than the control intervention. Nonetheless, these data demonstrate our ability to conduct serial CPX testing in a large study population with limited exercise capacity, supporting the use of CPX testing in Aim 2 of the proposed investigations.

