### **Expected outcomes:**

Specific Aim 1: FMD and RHI at 24 hours post-transfusion with saRBCs will be lower than following transfusion of fresh RBCs in the same patient.

Specific Aim 2: Exercise tolerance and VO2Max will increase following fresh RBC transfusions; in contrast, transfusion of saRBC will either lead to a lesser increase in these markers or will produce an actual decrease in these parameters.

Secondary Endpoints: Markers of oxidative stress (glutathione and cysteine redox ratios) and inflammatory markers will show a greater increase following saRBC transfusion than after fresh transfusions.

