### **Statistical considerations:**

Sample size justification for Aim 1: Subject numbers are based on the primary objective (Aim 1) of measuring change in FMD (%) with transfusion. For sample size calculations, we use the paired t-test statistic and assume a two-sided test with  $\alpha=0.05$  and power = 0.8. Based on the FMD changes we observed in transfused hospitalized patients (see preliminary data) of 2.4% with saRBC transfusion and a standard deviation of FMD in our lab of 3.11%, with a sample size of 24 we have power to observe a 0.85% change in FMD with blood transfusion. This is a clinically meaningful change.

Sample size justification for Aim 2: Subject numbers are based on the primary objective of measuring change in VO2Max with transfusion of fresh vs saRBCs (Aim 2). A sample size of 24 achieves 86% power to detect a VO2Max difference of 130 ml/min between fresh and saRBC transfusions. These calculations are based on a mean of 1100 and the alternative hypothesis mean of 1230 with an estimated standard deviation of 190.0 and with a significance level (alpha) of 0.05 using a two-sided Wilcoxon test assuming that the actual distribution is normal. This calculation is based on published VO2Max responses to exercise in an anemic population.

Statistical analysis will be performed in consultation with faculty statisticians within the Emory Clinical Cardiovascular Research Institute. Descriptive statistics will be performed initially by calculating means, standard deviation, range, descriptive plots, and box-plot histograms for each variable. This will assist in determining distributional properties of the outcome variable and the choice of appropriate subsequent analytical approaches (parametric vs non-parametric). For most analyses, we will use a generalized linear mixed model to analyze these data provided that outcomes are normally distributed. Otherwise we will use transformation methods. Given that there are multiple hypotheses with multiple outcomes it is necessary to adjust for multiple comparisons. With the proposed sample size, we will not adjust for multiple comparisons with different outcomes but will adjust for comparisons within each outcome. The sample size may be too small for certain outcomes given the heterogeneity of subjects: therefore we will interpret results carefully, particularly with secondary outcomes. In such cases we will report the confidence intervals.

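### Aim 1 primary endpoint: 24-hour FMD is implied but not designated, the role of pre-transfusion FMD is left open, and the 0.85% detectable change does not follow from SD 3.11 with 24 patients

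*Combined protocol and SAP*

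**What the plan says.** The Aim 1 endpoint, given in identical terms in both statements of the Specific Aims, is: "The primary endpoint of this Aim is the change in FMD with fresh vs. saRBC transfusion". Study Design sets the readings: "Vascular function will be assessed prior to transfusion as well as 1 hour and 24 hours after blood transfusion".

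Three places lean towards 24 hours:
- Preliminary Data, on the hospitalised patients given stored blood: "by 24 hours after transfusion the continued reduction in FMD was statistically significant".
- Study Schedule, Visit #2, which justifies the day-after visits because "impairment of NO-mediated vasodilation by saRBC transfusion was greatest 24 hours after transfusion".
- Expected outcomes, Aim 1: "FMD and RHI at 24 hours post-transfusion with saRBCs will be lower than following transfusion of fresh RBCs in the same patient".

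The last is a comparison of levels. The note to Figure 3, by contrast, reports "p<0.05 for change from baseline FMD".

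Statistical considerations says "For most analyses, we will use a generalized linear mixed model to analyze these data", without listing model terms. It promises multiplicity adjustment within each outcome but not across outcomes. The Aim 1 sample size rests on a paired t-test, two-sided 0.05 and 80% power, with "a standard deviation of FMD in our lab of 3.11%, with a sample size of 24 we have power to observe a 0.85% change". The plan words this as an FMD change following transfusion and describes it as clinically meaningful.

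**The concern.** Two matters are left open for the primary analysis: which post-transfusion reading counts, and whether pre-transfusion FMD is subtracted, used as a covariate or ignored. In a randomised crossover without carry-over, these contrasts estimate the same mean effect, so the issue is specification and precision. It still matters with 24 patients. A difference of two change scores carries the noise of four readings and does badly if readings in the same period correlate little better than readings in different periods. A comparison of 24-hour levels ignores the pre-transfusion readings and does badly in the opposite case. The documents report no correlation between the pre-transfusion and 24-hour readings, so neither can be chosen safely in advance.

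The 0.85% figure is a second matter. If the trial cannot detect an effect of that size with the stated power, a null result could be misread as excluding an effect that the plan itself calls meaningful.

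**Working it through.** **Inputs.** From Statistical considerations: n=24, paired t-test, two-sided 0.05, 80% power, SD 3.11, detectable change 0.85, effect in hospitalised patients 2.4. From Study Measurements, FMD reproducibility: r=0.75 between assessments about 8 days apart in 11 subjects. The Fisher 95% interval is tanh(atanh 0.75 ± 1.96/√8) = 0.27 to 0.93. From the Specific Aims text: these patients are transfused every 2 to 4 weeks, a longer gap than 8 days.

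**Step 1: the plan's own figure** (noncentral t, 23 df). The detectable difference at 80% power is 0.597 × SD of the paired difference.
- If 3.11 is that SD: 0.597 × 3.11 = 1.86. Power at 0.85 is 25%, and 108 patients would be needed.
- If 3.11 is a single-reading SD with r=0.75: paired SD = 3.11 × √(2 × 0.25) = 2.20, detectable 1.31. Power at 0.85 is 44%, and 55 patients would be needed.
- For 0.85 with 24 patients, the paired SD must be 0.85/0.597 = 1.42.

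Neither reading of the stated SD gives 0.85.

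**Step 2: three possible contrasts.** Let s be the single-reading SD, rw the correlation between the pre-transfusion and 24-hour readings in the same period, and rb the correlation between readings in different periods. Assume that s is equal at all readings and that all cross-period correlations equal rb.
- Difference of change scores: variance = 4s²(1−rw)
- Difference of 24-hour levels: variance = 2s²(1−rb)
- Levels adjusted for the pre-transfusion difference: variance = 2s²(1−rb)(1−b²)(1+1/(n−4)), with b=(rw−rb)/(1−rb). The last factor is the cost of estimating the slope.

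Period is in every model, so df are 22, 22 and 21. Worked case with s=3.11, rb=0.75, rw=0.85: b = 0.10/0.25 = 0.4; the SDs are 2.41 (change), 2.20 (level) and 2.20 × √(0.84 × 1.05) = 2.07 (adjusted).

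Detectable difference at 80% power, s=3.11:

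| rb | rw | Change score | 24-h level | Adjusted |
|---|---|---|---|---|
| 0.75 | 0.75 | 1.86 | 1.32 | 1.35 |
| 0.75 | 0.85 | 1.44 | 1.32 | 1.24 |
| 0.75 | 0.90 | 1.18 | 1.32 | 1.08 |
| 0.75 | 0.95 | 0.83 | 1.32 | 0.81 |
| 0.50 | 0.75 | 1.86 | 1.86 | 1.66 |
| 0.50 | 0.95 | 0.83 | 1.86 | 0.83 |
| 0.27 | 0.75 | 1.86 | 2.25 | 1.74 |
| 0.27 | 0.95 | 0.83 | 2.25 | 0.84 |
| 0.93 | 0.95 | 0.83 | 0.70 | 0.69 |

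At rb=0.75 and rw = 0.75, 0.85, 0.90, 0.95, adjustment cuts the variance by 47, 26, 16 and 5% against change scores, and by −5, 12, 33 and 62% against levels. It overtakes levels once rw exceeds about 0.80. The worst case for adjustment is rw=rb: for example, with both at 0.5 it detects 1.91 against 1.86 for levels, under 3% worse. Simulation of the crossover at rb=0.75 (20,000 runs) agreed with these variances and powers, and null rejection was 4.6 to 5.4%.

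**Step 3: when 0.85 is reachable.** At rb=0.75 and s=3.11, the adjusted analysis detects 0.85 only if rw is about 0.94 or more. Otherwise s must be smaller: about 2.1 at rw=0.85, or 2.4 at rw=0.90.

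**Step 4: at the hospitalised-patient effect of 2.4.** With rb=0.75, all three analyses have at least 95% power. Levels alone fall to 85% at rb=0.27.

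**The case against.** The time point is nearly settled: the Aim 1 expectation is stated only at 24 hours, and the schedule justifies the day-after visits on that ground. Designating it is one line. This stands.

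The within-outcome multiplicity clause could be read as covering the 1-hour and 24-hour readings together. It limits type I error, but it names no primary contrast, and the sample size uses the full 0.05. Splitting alpha equally over two times at r=0.75 (23 df) would raise the detectable difference from 1.31 to 1.47 for levels and from 1.86 to 2.07 for change scores.

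A mixed model that treats pre-transfusion FMD as a repeated outcome with a common mean could match the adjusted precision. That is true, but only with terms that the plan does not state. Adjustment is therefore one sound option among others, and its gain depends on an unreported correlation.

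The 0.85% may have come from the reproducibility data: √(1.26² + 0.76²) = 1.47 gives 0.84 by a normal approximation, or 0.88 by t. This is inferred, and the plan cites 3.11. The same SD gives 1.24 for a difference of two changes. If those data imply a single-reading SD of 1.47/√0.5 = 2.08, the adjusted analysis detects 0.83 at rb=0.75, rw=0.85, so 0.85% is not out of reach. Nor is it at rb=0.90, where levels alone detect 0.83 even with s=3.11. The figure needs a stated basis.

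**Conclusion.** The concern holds. The firmest part is the 0.85% figure: the detectable difference is 1.86 or 1.31 points, depending on which SD 3.11 is, with 25% or 44% power at 0.85. The first pair needs no assumption about correlation; the second uses the laboratory's r=0.75.

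The endpoint wording is a specification gap with consequences for precision. It rests on equal SDs, equal cross-period correlations, and an rb taken from only 11 subjects over a shorter interval than the trial's. Within those limits, adjustment is the safe choice: it is never more than about 3% behind the best contrast. By comparison, change scores can be about 40% worse than levels (1.86 against 1.32), and levels more than twice as bad as change scores (2.25 against 0.83).

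The choice matters mainly for effects well below 2.4 points. Such effects are plausible here, because Potential Limitations concedes that these outpatients may have less endothelial dysfunction than the hospitalised group, and 2.4 was a change after stored blood alone. This should be corrected before analysis; confidence is medium.

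**What to change.** 1. In both statements of Aim 1, designate FMD at 24 hours (Visits 2 and 4) as the single primary time point, tested at two-sided 0.05, with 1-hour FMD secondary. State that the within-outcome multiplicity clause does not apply to this single test. Correct the Visit #2 text that calls the post-transfusion visits #3 and #5, since the schedule has four visits.
2. In Statistical considerations, define the primary analysis as the within-patient fresh-minus-stored difference in 24-hour FMD, adjusted for the within-patient difference in pre-transfusion FMD (Visits 1 and 3) and for period. Align Expected outcomes with it. A fully specified mixed model giving the same contrast would serve.
3. Say which SD 3.11 is, and whether 0.85% means the fresh-minus-stored contrast or a pre-to-post change. Restate the detectable difference from the SD of the chosen contrast, with a range over the unknown correlations.

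The cost is wording only; no visit, test or patient is added. If the baseline difference is uninformative, adjustment costs about 5% in variance and one degree of freedom. It gains almost nothing over change scores when rw is near 0.95 and rb is 0.5 or less. The second-period baseline follows the first randomised transfusion, so carry-over could affect the covariate, as it would a change score.
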